OVERVIEW: I'd like to ask you some questions about the past week. How have you been feeling since last (DAY OF THE WEEK)? IF OUTPATIENT: Have you been working? IF NOT: Why not?

MILD: Occurs irregularly and for short periods of time.
MODERATE: Occurs more constantly and of longer duration, requiring considerable effort on the part of the subject to cope with it.
SEVERE: Continuous and dominates the subject's life.
VERY SEVERE: Incapacitating.

In the last week, how much have you been worrying? ANXIOUS MOOD (worries, anticipation of the worst, fearful anticipation, irritability):

How much have you been thinking about the worst that can happen, or been afraid of what's going to happen?
0 – not present
1 – mild
2 – moderate
3 – severe
4 – very severe

Have you been feeling especially irritable this past week?

IF SCORED 1-4 ABOVE, ASK: How long have you been feeling this way?

In the past week, how much have you felt tense? Have you gotten tired easily? TENSION (feelings of tension, fatigability, startle response, moved to tears easily, trembling, feelings of restlessness, inability to relax):

How much have you been bothered by any of these things: being startled easily, crying easily, trembling, feeling restless, not being able to relax? For each SX: How bad has that been this past week?
0 – not present
1 – mild
2 – moderate
3 – severe
4 – very severe

This past week, have you been afraid of the dark, of strangers, of being left alone, of animals, of traffic, or of crowds? IF YES: How afraid? FEARS (of the dark, of strangers, of being left alone, of animals, of traffic, of crowds):

0 – not present
1 – mild
2 – moderate
3 – severe
4 – very severe

SIGH-A	MILD:	Occurs irregularly and for short periods of time.
	MODERATE:	Occurs more constantly and of longer duration, requiring considerable effort on the part of the subject to cope with it.
	SEVERE:	Continuous and dominates the subject's life.
	VERY SEVERE:	Incapacitating.

In the last week, have you had trouble falling asleep, or had broken sleep, unsatisfying sleep and being tired when you wake up, bad dreams, or nightmares? FOR EACH SX: How bad has that been?

INSOMNIA (difficulty in falling asleep, broken sleep, unsatisfying sleep and fatigue on waking, dreams, nightmares, night terrors):

- 0 – not present
- 1 – mild
- 2 – moderate
- 3 – severe
- 4 – very severe

In the last week, have you had trouble concentrating, or trouble remembering things? How much?

INTELLECTUAL (difficulty in concentrating, poor memory):

- 0 – not present
- 1 – mild
- 2 – moderate
- 3 – severe
- 4 – very severe

In the past week, have you felt depressed?

DEPRESSED MOOD (loss of interest, lack of pleasure in hobbies, depression, early waking, diurnal swing):

Have you been less interested in things, or not enjoying things you usually enjoy doing?

- 0 – not present
- 1 – mild
- 2 – moderate
- 3 – severe
- 4 – very severe

This past week, what time have you been waking up in the morning for the last time? (Is that with an alarm clock, or do you just wake up yourself?)

This past week, have you been feeling better or worse at any particular time of day – morning or evening? IF VARIATION: How much worse do you feel in the (MORNING OR EVENING)? IF UNSURE: A little bit worse or a lot worse?

SIGH-A	MILD:	Occurs irregularly and for short periods of time.
	MODERATE:	Occurs more constantly and of longer duration, requiring considerable effort on the part of the subject to cope with it.
	SEVERE:	Continuous and dominates the subject's life.
	VERY SEVERE:	Incapacitating.

In the last week, have you been bothered by aches and pains, muscle twitching, stiffness or sudden muscle jerks? SOMATIC (MUSCULAR) (pain and aches, twitching, stiffness, myoclonic jerk, grinding of teeth, unsteady voice, increased muscular tone):

How about grinding your teeth, having an unsteady voice, or your muscles being tense?

0 – not present
 1 – mild
 2 – moderate
 3 – severe
 4 – very severe

IF YES: How bad has that been? (How much has it bothered you?)

In the past week, have you had ringing in your ears, blurred vision, hot or cold flashes, feelings of weakness, or pricking sensation? IF YES: How bad has that been? (How much has it bothered you?) SOMATIC (SENSORY) (tinnitus, blurring of vision, hot and cold flashes, feelings of weakness, pricking sensation):

0 – not present
 1 – mild
 2 – moderate
 3 – severe
 4 – very severe

In the past week, has your heart raced, skipped, or pounded? Have you had pain in your chest, throbbing blood vessels, or fainting feelings? IF YES: How bad has that been? CARDIOVASCULAR SYMPTOMS (tachycardia, palpitations, missing beats, pain in chest, throbbing of vessels, fainting feelings):

0 – not present
 1 – mild
 2 – moderate
 3 – severe
 4 – very severe

In the last week, have you had pressure or tightness in your chest, or choking feelings? IF YES: How bad has that been? RESPIRATORY SYMPTOMS (pressure or constriction in chest, choking feelings, sighing, dyspnea):

What about sighing, or shortness of breath? IF YES: How bad has that been?

0 – not present
 1 – mild
 2 – moderate
 3 – severe
 4 – very severe

SIGH-A	MILD:	Occurs irregularly and for short periods of time.
	MODERATE:	Occurs more constantly and of longer duration, requiring considerable effort on the part of the subject to cope with it.
	SEVERE:	Continuous and dominates the subject's life.
	VERY SEVERE:	Incapacitating.

In the last week, have you had trouble swallowing? Have you had stomach pain or fullness, gas, nausea, vomiting, burning or rumbling in your stomach, loose bowels, or constipation. IF YES: How bad has that been? Have you lost weight in the past week? IF YES: How much? Have you been trying to lose weight? DO NOT RATE LOSS OF WEIGHT DUE TO DIETING.

GASTROINTESTINAL SYMPTOMS (difficulty in swallowing, wind, abdominal pain, burning sensations, abdominal fullness, nausea, borborygmi, looseness of bowels, loss of weight, constipation):

0 – not present
1 – mild
2 – moderate
3 – severe
4 – very severe

In the past week, have you had to urinate frequently? Have you had the urge to?

GENITOURINARY SYMPTOMS (frequency of micturition, urgency of micturition, amenorrhea, menorrhagia, development of frigidity, premature ejaculation, loss of libido, impotence):

How has your interest in sex been in the past week? (Here, I'm not asking about performance but about your interest in sex. How much did you think about it?).

0 – not present
1 – mild
2 – moderate
3 – severe
4 – very severe

FOR WOMEN: Have you had trouble having an orgasm in the past week? (When did that start?) Have you had your period in the last month or so? IF NOT: Do you know why not? IF YES: Was it especially heavy?

FOR MEN: Have you had trouble with premature ejaculation (coming too soon) in the past week? How about trouble keeping an erection? (When did that start?)

In the past week, has your mouth been dry? Have you had any flushing in your face, or have you been pale? Have you felt lightheaded, or had any tension headaches? How about feeling the hair rise on your arms, the back of your neck, or your head? Have you tended to sweat a lot in the past week? FOR EACH SX: How bad has that been?

AUTONOMIC SYMPTOMS (dry mouth, flushing, pallor, tendency to sweat, giddiness, tension headache, raising of hair):

0 – not present
1 – mild
2 – moderate
3 – severe
4 – very severe

SIGH-A	MILD:	Occurs irregularly and for short periods of time.
	MODERATE:	Occurs more constantly and of longer duration, requiring considerable effort on the part of the subject to cope with it.
	SEVERE:	Continuous and dominates the subject's life.
	VERY SEVERE:	Incapacitating.

RATING BASED ON OBSERVATION

BEHAVIOR AT INTERVIEW (fidgeting, restless or pacing, tremor of hands, furrowed brow, strained face, sighing or rapid respiration, facial pallor, swallowing, belching, brisk tendon jerks, dilated pupils, exophthalmos, etc.)

- 0 – not present
- 1 – mild
- 2 – moderate
- 3 – severe
- 4 – very severe

TOTAL 14-ITEM HAMILTON ANXIETY SCORE

SAMPLE - DO NOT USE

**APPENDIX J. CLINICAL GLOBAL IMPRESSION SCALE - SEVERITY
(CGI-S) - SAMPLE**

Rater Initials			Time Performed (24 hours)				Has the rater changed from the previous assessment?				
			_____ : _____				Yes 		No 		N/A 
Subject Initials:			Subject ID No.				Date of Assessment (DD/MMM/YYYY)				Visit No.

Clinical Global Impression – Severity (CGI-S) Scale

Considering your total clinical experience with this particular population, how mentally ill is the patient at this time?

- 0 = Not assessed
- 1 = Normal, not at all ill
- 2 = Borderline mentally ill
- 3 = Mildly ill
- 4 = Moderately ill
- 5 = Markedly ill
- 6 = Severely ill
- 7 = Among the most extremely ill patients

Rater Signature: _____ Date: _____

SAMPLE - DO NOT USE

6Busner, J., Targum, S., The Clinical Global Impressions scale: *Applying a Research Tool in Clinical Practice*. Psychiatry, 2007; 4(7):28-37 as adapted from Kay, Stanley R., *Positive and Negative Symptoms in Schizophrenia: Assessment and Research*. Clinical and Experimental Psychiatry, Monograph No. 5. Brunner/Mazel, 1991.

AESI	Adverse Event of Special Interest		
ALP	Alkaline Phosphatase		
ALT	Alanine Aminotransferase		
AST	Aspartate Aminotransferase		
BDZ	Benzodiazapine		
BMI	Body Mass Index		
BUP	Buprenorphine		
CGI-S	Clinical Global Impression - Severity		
CI	Confidence Interval		
CNS	Central Nervous System		
COWS	Clinical Opiate Withdrawal Scale		
CRF	Case Report Form		
C-SSRS	Columbia Suicide Severity Rating Scale		
DILI	Drug Induced Liver Injury		
ECG	Electrocardiogram		
eDISH	Evaluation of Drug-induced Serious Hepatotoxicity		
EOT	End of Treatment		
ET	Early Termination		
FAS	Full Analysis Set		
HAM-A	Hamilton Rating Scale for Anxiety		
LLRR	Lower Limit of Reference Range		
MADRS	Montgomery-Asberg Depression Rating Scale		
MAOI	Moclobemide		
MDD	Major Depressive Disorder		
MDE	Major Depressive Episode		
MedDRA	Medical Dictionary for Regulatory Activities		
NDA	New Drug Application		
PCS	Potentially Clinically Significant		

Abbreviation	Definition
PDEAE	Post-discontinuation Emergent Adverse Event
PLI	Prospective Lead-in
PT	Preferred Term
QTcF	QTcF – Fridericia's Correction Formula
SAE	Serious Adverse Event
SAM	Samidorphan
SAP	Statistical Analysis Plan
SD	Standard Deviation
SE	Standard Error
SNRI	Serotonin-norepinephrine Reuptake Inhibitor
SOC	System Organ Class
SSRI	Selective Serotonin Reuptake Inhibitor
TBILI	Total Bilirubin
TCA	Tricyclic Antidepressant
TEAE	Treatment Emergent Adverse Events
ULRR	Upper Limit of Reference Range
VS	Vital Sign
WHO-ATC	World Health Organization Anatomical Therapeutic Chemical

1. INTRODUCTION

This statistical analysis plan (SAP) describes the statistical methods and data presentation to be used for analyzing and reporting efficacy and safety data for study ALK5461-208 for the adjunctive treatment of Major Depressive Disorder (MDD) at study completion. This document has been prepared based on Alkermes ALK5461-208 study protocol amendment 3 (dated 03 March 2016) [1].

1.1. Study Objectives

The objective of this study is to assess the long-term safety and tolerability of ALKS 5461 for use as an adjunctive therapy to antidepressants for the treatment of MDD.

1.2. Summary of the Study Design and Schedule of Assessments

This is a Phase 3, multicenter, multinational, study to evaluate the long-term safety and tolerability, and to explore treatment effect of 52 weeks of ALKS 5461 administration for use as an adjunctive therapy to antidepressants (ADT) for the treatment of MDD in subjects who have had 1 or 2 inadequate response to an approved ADT in the current MDE.

ALKS 5461 was studied at a dose of 2 mg buprenorphine (BUP):2 mg samidorphan (SAM). Note that ALKS 5461 dose levels are referred to as doses of BUP/SAM expressed as weight in mg (eg, a 2 mg BUP:2 mg SAM dose is expressed as ALKS 5461 2/2).

All subjects in the study had been treated with an adequate dose of an approved ADT for at least 8 weeks, at a stable dose over the last 4 weeks prior to study entry.

Subjects will enter into the study in one of three ways, based on their prior experience with an ALKS 5461 study:

- 1. New Subjects: those who have not participated in a prior study of ALKS 5461 within 2 years.
- 2. Continuing Subjects: those who have completed the treatment period of study ALK5461-205, ALK5461-206, ALK5461-207, or ALK5461-210 within the past 10 days. Since some of these antecedent studies were randomized placebo-controlled studies, these subjects may or may not have received ALKS 5461 in the prior study.
- 3. Lead-in Subjects: those who participated in study ALK5461-205, ALK5461-206, or ALK5461-207 within the past 10 days, and met the criteria for response to ADT during the prospective lead-in (PLI) period of that antecedent study, but did not meet the criteria for remission. These subjects were not eligible for entry into the double-blind treatment period in the antecedent and received neither placebo nor ALKS 5461 in the antecedent study.

All New Subjects will be initially evaluated for eligibility at screening (Visit 1), to occur up to 28 days prior to Visit 2.

For Continuing Subjects and Lead-in Subjects, Visit 2 will be the first visit of this study and there will not be a separate screening visit. Identical assessments taken at the subject's last visit

[figure not shown]
of the antecedent study do not need to be repeated at Visit 2 of this study unless more than 10 days elapses between these visits.

At Visit 2, all eligible, consenting subjects will begin the treatment period. Subjects entering the study already receiving ALKS 5461 will not require titration; all other subjects will require a 1-week ALKS 5461 titration period. Depending on the antecedent study, the titration may be blinded per blinding schemes as described in the protocol. From Week 2 to 52, all participating subjects will take ALKS 5461 2/2 and an approved ADT, with allowable ALKS 5461 dose adjustments for tolerability as described in the protocol.

During the 52-week treatment period, subjects will return to the clinic for periodic scheduled visits (Visits 2-14) at which safety, tolerability, and treatment effect over time will be assessed.

A 4-week safety follow-up period will occur following the ALKS 5461 treatment period. During the 4-week follow-up period, there are a total of 4 clinic visits (Visits 15-18), as well as 7 safety assessments by phone. Please refer to the protocol for a detailed schedule of assessments. A brief schematic of study design is provided in Figure 1. A summary of the schedule of safety assessments is presented in Table 1.

Figure 1: Study Design Schematic

Abbreviations: EOS=end of study; EOT=end of treatment; ET=early termination; PLI=prospective lead-in; V=visit

Table 1: Schedule of Safety Assessments

Study Number	Dosing Schedule (Days)	Vital Signs ^a	Clinical Laboratory Testing ^b	12-Lead ECG	C-SSRS ^d	COWS ^e	AEs
ALK5461- 208	Treatment: 1-365 (1 year) Titration: 1-7 (1 week) Safety Follow Up: 366- 393 (1 month)	Screening, Days 1°, 8, 15, 29, 43, 57, 99, 141, 183, 225, 267, 309, 365, 366, 372, 379, 393	Screening, Days 1°, 8, 99, 183, 267, 365, 393	Screening, Days 1°, 8, 183, 365, 393	Screening, Days 1°, 8, 15, 29, 43, 57, 99, 141, 183, 225, 267, 309, 365, 366, 372, 379, 393	Days 365, 366, 372, 379, 393 ^e	Throughout

Abbreviations: ECG=electrocardiogram; C-SSRS=Columbia-Suicide Severity Rating Scale; COWS=Clinical Opiate Withdrawal Scale; AEs=Adverse Events

1.3. Criteria for Evaluation

Safety and Tolerability:

The following assessments will be collected to measure safety and tolerability throughout the study:

- Adverse events (AEs)
- Vital signs (VS)
- Weight
- Clinical laboratory parameters (chemistry, hematology, and urinalysis)
- Electrocardiogram (ECG) parameters
- Columbia Suicide Severity Rating Scale (C-SSRS)
- Clinical Opiate Withdrawal Scale (COWS)

Efficacy:

The following assessments will be collected to measure treatment effect throughout the study:

- Montgomery-Asberg Depression Rating Scale (MADRS)
- Hamilton Rating Scale for Anxiety (HAM-A)
- Clinical Global Impression Severity (CGI-S)

^a Vital signs included weight, oral temperature, supine respiratory rate, blood pressure, and heart rate.

^b Chemistry, hematology, and urinalysis.

^c Conducted predose.

d At screening the "Baseline" version of the C-SSRS was administered and at all other visits the "Since Last Visit" version was administered.

^e COWS was administered by a medical professional.

2. SAMPLE SIZE AND STATISTICAL POWER CONSIDERATION

Approximately 1,500 subjects will be enrolled in order to achieve at least 100 subjects with 12 months and 300 subjects with 6 months of exposure to ALKS 5461. Subjects will enter from four feeder studies or enter de novo. The antecedent studies included ALK5461-205, ALK5461-206, ALK5461-207, and ALK5461-210.

3. DATA ANALYSIS

3.1. General Statistical Methodology

The safety and efficacy endpoints will be summarized by prior ALKS 5461 exposure: no prior exposure to ALKS 5461 and prior exposure to ALKS 5461, as well as overall.

Subjects with no prior exposure to ALKS 5461 come from three sources: De Novo (i.e., New Subjects), PLI Failures (i.e., antecedent study Prospective Lead-in Subjects Failures) and Placebo (i.e., those who did not receive any active treatment in an antecedent study).

Prior exposure to ALKS 5461 subjects include Continuing Subjects who received active treatment (doses ALKS 5461 0.5/0.5, ALKS 5461 1/1, or ALKS 5461 2/2) in an antecedent study. Subjects with prior exposure are designated as such independent of the duration of exposure in the antecedent trial.

In general, summary statistics (n, mean, standard deviation [SD], median, minimum, and maximum for continuous variables, and number and percentage of subjects in each category for categorical variables) based on observed data will be provided by prior ALKS 5461 exposure and overall. Measurements collected from unscheduled visits or repeated assessments will not be included in the by-visit summary tables or figures, but will be included in categorical outlier analyses of post-baseline values and subject listings.

In general, only data collected during the ALK5461-208 study will be summarized even though the baseline may come from an antecedent study.

Last assessment during treatment period, defined as the last non-missing value from scheduled post-baseline visit during the treatment period (i.e., from Visit 2 to Visit 14, inclusive), will be included in the by-visit summary tables for both efficacy and safety endpoints as appropriate.

Source data for the summary tables will be presented as subject data listings. Please refer to Section 6.1 on the handling of data collected at an early termination visit.

3.2. Study Population

3.2.1. Definitions of Analysis Populations (Analysis Sets)

Safety Population consists of all subjects who receive at least 1 dose of study drug in the ALK5461-208 study.

An AE will be considered as a treatment emergent adverse event (TEAE) if it starts or worsens (if present at baseline) on or after the baseline during treatment period. An AE will be

considered as a post-discontinuation emergent adverse events (PDEAE) if it starts or worsens after the last dose date plus 1 day.

Post-discontinuation Safety Population consists of subjects in the Safety Population who have at least 1 post-discontinuation measurement. There will be two Post-discontinuation Safety Populations, one is used to analyze PDEAE, and the other is to analyze COWS, grouped by whether having had exposure to study drug in a prior controlled trial or had no prior exposure.

Post-discontinuation Safety Population for PDEAE consists of subjects who received at least 1 dose of study drug, and met one of the following criteria:

- Subjects who entered the Post-discontinuation Period and had a Post-discontinuation Visit
- Subjects who did not enter the Post-discontinuation Period, but had at least 1 PDEAE reported
- Subjects who died after either completing the treatment or having an Early Termination (ET) Visit

Post-discontinuation Safety Population for COWS consists of subjects who received at least 1 dose of study drug, had an adequate COWS baseline (defined as end of treatment [EOT] COWS assessment) and had at least 1 post-EOT COWS assessment, where an adequate EOT COWS is defined as having been performed within (≤) 2 days of last dose of study drug.

Full Analysis Set (FAS) consists of subjects in the Safety Population who have at least 1 post-baseline complete MADRS assessment.

The baseline for efficacy endpoints is defined as the last non-missing observation on or before the date of baseline visit (Visit 2) of ALKS 5461-208 study for subjects who are new to ALKS 5461 (ie, De Novo, PLI Failures, and Continuing Subjects who received placebo in antecedent study); or the last non-missing observation on or before the first dose of ALKS 5461 in antecedent study for Continuing Subjects who received any dose of ALKS 5461 (i.e., ALKS 5461 0.5/0.5, ALKS 5461 1/1, or ALKS 5461 2/2) in antecedent study.

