14.4. Demographics and Baseline Data

For all participating subjects, baseline is defined as Visit 2.

Demographics and baseline characteristics such as gender, age, race, weight, and baseline physical examination reports, vital signs, and clinical laboratory data will be summarized.

Psychiatric history including duration of current MDE, number of lifetime MDEs, number of prior lifetime ADT failures and number of ADT failures within the current MDE will be summarized.

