14.5. Efficacy Analyses

As stated in [Section 11](#), treatment effect over time will be assessed in an exploratory manner based on change from baseline in MADRS total score, HAM-A total score, and CGI-S score. Results will be presented as described in [Section 14.2](#) and the SAP.

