3.3. Demographics and Baseline Characteristics

For New Subjects only, demographic and baseline characteristics data (including MDD history) will be collected at screening visit. For Continuing Subjects and Lead-in Subjects, these data will be carried over from information recorded in the antecedent ALKS 5461 study in which they participated.

Demographics and baseline characteristics (age, gender, primary race, ethnicity, region (United States [US], non-US), duration of current MDE, ADT Class for current MDE, number of inadequate responses to ADT in the current MDE, lifetime number of MDEs, lifetime number of antidepressants, benzodiazepines (BDZ) use, opioid use, H1 antagonist use, height, weight, body mass index [BMI]) will be summarized by prior exposure to ALKS 5461, no prior exposure to ALKS 5461, and overall for the Safety Population. For no prior exposure to ALKS 5461, the group is divided further into 3 subgroups of De Novo, PLI Failures, and Placebo, as well as overall. Categories for missing data will be provided as necessary.

Baseline characteristics for efficacy measurments (MADRS-10 score, MADRS-6 score, HAM-A total score, CGI-S score and HAM-D total score) will be summarized by prior exposure to ALKS 5461, no prior exposure to ALKS 5461, and overall for the FAS Population. For no prior exposure to ALKS 5461, the group is divided further into three subgroups of De Novo, PLI Failures, and Placebo, as well as overall. The baseline for efficacy measurements is defined as the last non-missing value on or before the date of initiation of ALKS 5461 at any dose.

Medical and psychiatric history will be summarized using the number of observations and percentage of subjects reporting each category by prior ALKS 5461 exposure and overall for the Safety Population.

Demographic and baseline listings will be provided for all subjects.

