3.6.2. Efficacy Analysis

3.6.2.1. Montgomery-Asberg Depression Rating Scale (MADRS)

The MADRS measures the severity of depressive symptoms and consists of 10 items. The MADRS-10 is the sum of all 10 items and ranges from 0 to 60. The MADRS-6 is the sum of the following 6 items: item 1 reported sadness; item 2 apparent sadness; item 3 inner tension; item 7 lassitude; item 8 inability to feel; and item 9 pessimistic thoughts and ranges from 0 to 36. Section 6.2 describes the handling of MADRS-10 if any of the items of the MADRS is missing.

The following endpoints will be assessed:

- Change from baseline in MADRS-10 and MADRS-6 score
- Proportion of subjects demonstrating MADRS treatment response, defined as a ≥50% reduction in MADRS-10 from baseline
- Proportion of subjects achieving remission, defined as a MADRS-10 of \leq 10

Descriptive summary statistics of baseline MADRS-10 and MADRS-6 score and change from baseline at each visit including the last assessment during treatment period will be provided by prior ALKS 5461 exposure and overall based on observed data. In addition, the figures of MADRS-10 and MADRS-6 score (including standard error), mean change from baseline (including standard error) over time including the last assessment during treatment period will be provided by prior ALKS 5461 exposure and overall based on observed data.

The responder and remission endpoints are derived based on the observed MADRS-10. The number and percentage of subjects demonstrating MADRS-10 treatment response and remission by visit including the last assessment during treatment period will be provided based on FAS. The figures of MADRS-10 responder rate and MADRS-10 remission rate over time including the last assessment during treatment period will be provided by prior ALKS 5461 exposure and overall.

The individual MADRS item scores will not be summarized but will be included in the subject listing.

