5. CHANGES IN CONDUCT OR PLANNED ANALYSES FROM THE PROTOCOL

N/A.

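### For prior-exposed subjects the SAP measures efficacy change from before their first ALKS 5461 dose, not from the protocol's Visit 2 baseline, pools this into the overall results, and declares no departure

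*SAP*

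**What the plan says.** Protocol 14.4: "For all participating subjects, baseline is defined as Visit 2". It makes no exception for efficacy. Protocol 14.5 then assesses treatment effect over time "based on change from baseline in MADRS total score, HAM-A total score, and CGI-S score".

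SAP 3.2.1 splits the efficacy baseline by entry route. It counts De Novo subjects, PLI Failures and Continuing Subjects who had placebo as not yet exposed, and their baseline is "the last non-missing observation on or before the date of baseline visit (Visit 2) of ALKS 5461-208 study for subjects who are new". Continuing Subjects who had active drug use "the last non-missing observation on or before the first dose of ALKS 5461 in antecedent study for Continuing Subjects who received any dose". SAP 3.3 states the general rule behind both: "The baseline for efficacy measurements is defined as the last non-missing value on or before the date of initiation of ALKS 5461 at any dose".

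SAP 3.1 reports results by "no prior exposure to ALKS 5461 and prior exposure to ALKS 5461, as well as overall". It also says that only data from this study are summarised, although a baseline may come from an antecedent study. SAP 3.6.2.1 adds an endpoint that depends on baseline: "Proportion of subjects demonstrating MADRS treatment response, defined as a ≥50% reduction in MADRS-10 from baseline".

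SAP Section 5, headed "CHANGES IN CONDUCT OR PLANNED ANALYSES FROM THE PROTOCOL", contains only N/A.

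**The concern.** The protocol fixes one time origin for everyone, the start of this study. The SAP fixes another, the first ALKS 5461 dose. The two coincide for subjects new to the drug and differ for prior-exposed subjects. As planned, the protocol-defined change from baseline is not produced for prior-exposed subjects or for the overall column, and a reader of Section 5 would not know this.

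At stake is what the long-term efficacy displays mean. An overall mean at Week 52 would average change since Visit 2 in some subjects with change since an earlier study in others, weighted by how many prior-exposed subjects happened to enrol and stay. From such a result a reader cannot separate improvement during this study from improvement brought into it.

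**Working it through.** **No figure to reproduce.** The study is uncontrolled and descriptive. The documents state no expected efficacy result, no antecedent MADRS scores and no planned share of prior-exposed subjects.

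**Identity.** Let X0 be the last score before the first ALKS 5461 dose, X2 the Visit 2 score and Xt the score at visit t.

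- SAP change = Xt − X0 = (Xt − X2) + (X2 − X0).
- Protocol change = Xt − X2.
- For subjects new to ALKS 5461, X0 = X2, so the two agree.
- For prior-exposed subjects they differ by X2 − X0, which arises wholly before Visit 2.

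Let s be the prior-exposed share of subjects observed at the visit, and d their mean improvement before Visit 2. The overall mean improvement under the SAP exceeds the Visit 2 version by s × d. If d is negative, it falls short.

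**Size of s × d in MADRS points (s and d are assumptions).**

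| s | d = 4 | d = 8 | d = 12 |
|---|---|---|---|
| 10% | 0.4 | 0.8 | 1.2 |
| 30% | 1.2 | 2.4 | 3.6 |
| 50% | 2.0 | 4.0 | 6.0 |

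**Response, single subjects (assumed scores).**

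- X0 = 30, X2 = 12, Xt = 15. From X0: (30 − 15)/30 = 50%, a responder. From X2 the subject has worsened by 3 points.
- X0 = 30, X2 = 8, Xt = 6. From X0: (30 − 6)/30 = 80%, a responder. From X2: (8 − 6)/8 = 25%, a non-responder, although a score of 6 is remission.

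The second case shows that Visit 2 has a weakness of its own.

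**Response, simulated (400,000 prior-exposed subjects per case; all inputs assumed).** Scores are limited to 0–60, with X0 mean 30 (SD 5) and change before Visit 2 with SD 8.

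- Essentially no mean change in this study (SD 6), d = 4, 8, 12: response is 14%, 25%, 38% from X0, against 4%, 7%, 10% from Visit 2. The overall rate differs by about 1 to 14 percentage points for s from 10% to 50%.
- Mean improvement of 6 points in this study (SD 8), d = 5 and 10: mean change is −10.7 and −15.2 from X0, against −5.7 and −5.3 from Visit 2. Response is 37% and 54%, against 24% and 33%. For s from 10% to 30%, the overall mean moves by 0.5 to 3.0 points and overall response by about 1 to 6 percentage points: 0.1 × (37 − 24) = 1.3 and 0.3 × (54 − 33) = 6.3.
- In that second setting, about 16% to 20% of prior-exposed remitters count as non-responders from Visit 2, because they enter with low scores.

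**What does not move.** The no-prior-exposure column is unchanged because X0 = X2. Remission is an absolute cut-off, and observed scores need no baseline. SAP Table 2 keeps the laboratory, vital-sign, ECG and C-SSRS baselines at Visit 2 for everyone.

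**Data.** Protocol Table 2 schedules MADRS, HAM-A and CGI-S at Visit 2, or allows an identical antecedent assessment no more than 10 days old to stand in. The Visit 2 analysis needs nothing new.

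**The case against.** The SAP applies one rule, not two. Everyone is measured from the last value before starting ALKS 5461, and SAP 3.2.1 works this out by entry route. Change since drug initiation is a coherent descriptive target, and SAP 3.1, 3.2.1 and 3.3 disclose it openly. Under Protocol Table 1, subjects who arrive from ALK5461-206, -207 or -210 on active drug have an on-drug score at Visit 2, so change from it describes maintenance rather than onset of effect. A pooled Visit 2 result therefore mixes off-drug and on-drug baselines, and a 50% reduction from an already treated score is a poor definition of response. Protocol 14.5 also leaves presentation partly to the SAP. Results are split by exposure, with observed scores and remission alongside.

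Most of this stands, and it is why the pre-drug analysis should be kept. It does not remove the conflict: Protocol 14.5 leaves presentation to the SAP, but 14.4 has already fixed the baseline. Nor do separate columns repair a pooled one.

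A reader might go further and infer that the overall result is inflated, or that prior exposure is favoured by construction. The documents do not support that. It requires net improvement before Visit 2, which is plausible but nowhere reported. A reader might also infer that the departure was concealed. It was not; it is missing only from Section 5.

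**Conclusion.** The conflict is established from the text: the protocol baseline is Visit 2 for all, while the SAP efficacy baseline is earlier for prior-exposed subjects. Both are pooled in the overall results, and Section 5 declares nothing. The consequence, a shift of s × d in the overall mean change, is exact arithmetic. Its direction and size are not established. The illustrations above, up to 6.0 MADRS points and 14 percentage points of response at the extreme, rest wholly on assumed shares, scores and SDs.

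The point is confined to MADRS, HAM-A and CGI-S change and MADRS response, in the prior-exposed and overall results. Efficacy is exploratory and the study's sole objective is safety, so no test or error rate is affected. It remains worth correcting, because the planned tables do not give the protocol's own measure of change and the remedy is cheap. The documents do not support the stronger reading that the pre-drug baseline is wrong and should be dropped.

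**What to change.** - In SAP 3.2.1, 3.3 and 3.6.2, add change and response from the protocol baseline (last non-missing value on or before Visit 2) for the prior-exposed and overall columns and figures. Use this version for any pooled overall change in this study.
- Keep the pre-ALKS 5461 baseline analysis for prior-exposed subjects, labelled as change since first ALKS 5461 dose.
- Footnote the tables: Visit 2 is an on-drug value for prior-exposed subjects who enter still taking ALKS 5461 (Protocol Table 1 shows this for entry from -206, -207 and -210, but not from -205 after its one-week discontinuation). Response from Visit 2 should be read with remission and observed scores.
- Replace N/A in SAP Section 5 with a statement of this departure and its reason.

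The cost is some SAP wording and one extra set of descriptive tables and figures from data already collected. Overall change and response may look less favourable.
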